7.1.1. Liver Chemistry Stopping Criteria

Interrupting study intervention based on elevated liver tests

The study intervention should be **interrupted** and close hepatic monitoring initiated (see Section 8.2.7), if 1 or more of the conditions in this table occur.

Elevation	Exception
ALT or AST >8x ULN	
ALT or AST >5x ULN for more than 2 weeks	
ALT or AST >3x ULN and either TBL >2x ULN or INR >1.5	For participants with Gilbert's syndrome: If baseline direct bilirubin is >0.5 mg/dL, then doubling of direct bilirubin should be used for drug interruption decisions rather than TBL>2x ULN.
ALT or AST >3x ULN with the appearance of fatigue, nausea, vomiting, right upper quadrant pain or tenderness, fever, rash, and/or eosinophilia (>5%)	
ALP >3x ULN, when the source of increased ALP is the liver	
ALP >2.5x ULN and TBL > 2x ULN	For participants with Gilbert's syndrome: If baseline direct bilirubin is >0.5 mg/dL then doubling of direct bilirubin should be used for drug interruption decisions rather than TBL>2x ULN.

ALP >2.5x ULN with the appearance of fatigue, nausea, vomiting, right upper quadrant pain or tenderness, fever, rash,	
and/or eosinophilia (>5%)	
Source: FDA 2009 and other consensus guidelines, with minor modifications.	

Resuming study intervention after elevated liver tests

Resumption of the study intervention can be considered only in consultation with the Lilly-designated medical monitor and only if the liver test results return to baseline and if a self-limited, non-drug etiology is identified. Otherwise, the study intervention should be permanently discontinued.

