In an AE overview table, the number and percentage of patients in the safety analysis set who experienced death, a serious adverse event (SAE), any TEAE, permanent discontinuation from study drug due to an AE, or a severe TEAE will be summarized by treatment group.

The number and percentage of patients with TEAEs will be summarized by treatment group in 2 formats listed below. For events that are gender specific, the denominator and computation of the percentage will only include patients from the given gender.

- By MedDRA PT nested within SOC with SOCs ordered alphabetically, and events ordered within each SOC by decreasing frequency in the 1000 mg of peresolimab Q4W treatment group
- By MedDRA PT with events ordered by decreasing frequency in the 1000 mg of peresolimab Q4W treatment group

AEs leading to permanent discontinuation of study drug and AEs leading to temporary interruption of study drug will also be summarized by treatment group using MedDRA PT nested within SOC. AE leading to temporary interruption of study drug will be identified using the response of "Drug Interrupted" in the question "What action taken with study treatment?" on the *Adverse Event* eCRF. Events will be ordered by decreasing frequency within SOC in 1000 mg of peresolimab Q4W treatment group.

A summary of temporary interruptions of study drug due to AEs will also be provided, showing the number of patients who experienced at least 1 temporary interruption and the number of temporary interruptions per patient with an interruption. Further, the duration of each temporary interruption (in days) and the cumulative duration of dose interruption (in days) using basic descriptive statistics (n, mean, SD, minimum, first quartile, median, third quartile, and maximum) will be displayed. Duration of study drug interruption will be calculated as: visit date of the missed dose – date of next resumed dose + 1, only if both dates are provided.

The number and percentage of patients with TEAEs will be summarized by maximum severity, SOC and PT by treatment using MedDRA PT ordered by decreasing frequency for the TEAEs. For each patient and TEAE, the maximum severity for the MedDRA level being displayed is the maximum postbaseline severity observed from all associated LLTs mapping to that MedDRA PT.

Adverse events of special interest include hypersensitivity, injection site reactions, infections, and malignancy.

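### AE-related dose interruptions with no resumed dose are counted but given no duration, so the duration and cumulative-duration summaries understate time off drug

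*SAP*

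**What the plan says.** SAP Section 4.6.2 identifies the events from the AE form: "AE leading to temporary interruption of study drug will be identified using the response of" *Drug Interrupted* to the question on action taken with study treatment. The summary is then described as "showing the number of patients who experienced at least 1 temporary interruption and the number of temporary interruptions per patient with an interruption". No condition about resumption is attached to these counts.

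The same paragraph asks for "the duration of each temporary interruption (in days) and the cumulative duration of dose interruption (in days) using basic descriptive statistics". The rule for it reads "Duration of study drug interruption will be calculated as: visit date of the missed dose" minus the "date of next resumed dose + 1, only if both dates are provided". The SAP version history lists this calculation as added in Version 3, so it is current text.

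No end date, censoring rule or imputation is given for an interruption without a resumed dose. The section does have a separate summary for permanent stops: "AEs leading to permanent discontinuation of study drug and AEs leading to temporary interruption of study drug will also be summarized by treatment group". It does not say where an interruption belongs if it later becomes permanent.

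The protocol provides for that path. Under Section 7.1.1, dosing interrupted for liver tests may restart only on stated conditions: "Otherwise, the study intervention should be permanently discontinued". Section 7.1.3 lists detectable HBV DNA under temporary discontinuation and makes the stop permanent if the result is confirmed.

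**The concern.** Whether an interruption receives a duration depends on whether, and when, dosing resumed, which is the quantity being summarized. The counts and the durations in one table then describe different sets of interruptions.

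For the cumulative total the direction is certain: real off-drug time is left out and nothing replaces it. For the mean, the direction depends on how long the excluded interruptions had lasted when observation ended. An arm with more unresumed interruptions loses more time, so the arms are not described on the same footing.

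Exposure does not make up for this. SAP Section 4.6.1 runs exposure from first dose to last dose or discontinuation and deducts no gaps. The weekly compliance summary in Section 6.2 shows missed injections but does not attribute them to AEs.

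**Working it through.** The documents state no interruption rate or duration, so there is no plan figure to reproduce.

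**1. Which interruptions enter which statistic (SAP 4.6.2)**

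| Statistic | Condition in the text | Interruption with no resumed dose |
|---|---|---|
| Patients with an interruption; interruptions per patient | Response is *Drug Interrupted* | Included while the response stands |
| Duration of each interruption | Both dates present | Excluded |
| Cumulative duration | Built from those durations | Adds nothing |

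Other parts of the SAP treat open records differently. Section 4.6.2.4 censors an infectious AE that is still open at completion or early discontinuation. Section 4.6.4.4 censors time to treatment-emergent ADA at the last assessment.

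**2. Date arithmetic**

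Take a missed dose on Day 29 and resumption on Day 57.

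- As printed: 29 − 57 + 1 = −27 days.
- In the other order: 57 − 29 + 1 = 29 days.

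The printed order gives zero if dosing resumes the next day and a negative value for any later resumption. Correcting it leaves the exclusion in place.

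**3. Illustration of size**

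From the SAP: 4-weekly dosing arms, and a Treatment Period ending at Visit 18 (Week 60). Assumed, not in the documents:

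- interruptions start with equal probability at the 14 visits from Week 4 to Week 56;
- Week 56 is the last dose;
- underlying durations are exponential with mean m weeks, rounded up to the next 4-weekly visit;
- every patient would eventually resume.

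Write q = exp(−4/m), and let n = 1, …, 14 be the number of 4-week steps from the start of the interruption to Week 60.

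- Share with no duration: P = (1 − q^14) / [14(1 − q)]
- Mean with open interruptions ended at Week 60: F = (4/14) × Σ(1 − q^n)/(1 − q)
- Mean observed length of the excluded: X = 4 × Σ n·q^(n−1) / Σ q^(n−1)
- Mean under the SAP rule, with the subtraction corrected: (F − P·X)/(1 − P)
- Share of observed off-drug time lost: P·X/F

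For m = 8, q = 0.6065:

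- P = 0.9991/(14 × 0.3935) = 0.181
- F = (4/14) × 12.460/0.3935 = 9.05
- X = 4 × 6.421/2.539 = 10.11
- SAP mean = (9.05 − 0.1814 × 10.11)/0.8186 = 8.81
- Time lost = 0.1814 × 10.11/9.05 = 20%

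| m (weeks) | No duration | SAP-rule mean (weeks) | Mean with open ones ended at Week 60 | Excluded: mean observed | Off-drug time lost |
|---|---|---|---|---|---|
| 4 | 11% | 6.03 | 6.06 | 6.33 | 12% |
| 8 | 18% | 8.81 | 9.05 | 10.11 | 20% |
| 12 | 25% | 10.92 | 11.59 | 13.58 | 29% |
| 24 | 42% | 14.43 | 16.79 | 20.04 | 50% |

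Simulating the same model agrees to within 0.1 week.

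The excluded interruptions are somewhat longer on average, but only 37% to 56% of them exceed the SAP-rule mean. For m = 8, 39% of the excluded start at Week 56 and have just 4 weeks observed.

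**4. Adding interruptions that never resume**

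Keep the same visits, with an assumed 0.5 chance of resuming at each one. Let u be the assumed share never resumed, all remaining in the count.

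- With q = 0.5 the share open at the end of dosing is 0.143, so the share without a duration is u + (1 − u) × 0.143. For u = 0/10/20/30% this is 14/23/31/40%.
- The SAP-rule mean stays at about 52 days throughout.
- A never-resumed interruption run to Week 60 averages 30 weeks, or 211 days with the extra day. The others average 53 days. The overall mean is 53(1 − u) + 211u, which is 53/69/85/100 days.

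These last figures are upper values, because a permanent-discontinuation date before Week 60 would end the interruption sooner.

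**The case against.** The strongest defence is that the table concerns *temporary* interruptions. Limiting its durations to completed ones is a legitimate choice, and the SAP states the condition openly. Permanent discontinuations due to AEs have their own overview line, summary by preferred term and listing, so these patients do not vanish from safety reporting. The duration statistics include n, so a reader could see a shortfall against the counts. All safety data are descriptive and no decision rule uses this table.

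Most of that stands and limits the importance of the point. It does not restore the lost time: the permanent-discontinuation summaries count events, not days off drug. Nor does it cover an interruption that was still open when scheduled dosing ended.

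Three stronger readings are tempting, and the documents do not support them.

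- **The rule drops the longest interruptions.** One that starts near the last dose is open but short, and the both-dates condition also drops records that lack the missed-dose date.
- **The shortfall is the gap to the full underlying duration.** For m = 24 that mean is 4/(1 − q) = 26.1 weeks against 14.43, but it includes time after Week 60, outside the Treatment Period.
- **Every never-resumed case is in the count.** If the form response is changed to a permanent stop, the case moves to the other summary. The SAP is silent on this.

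**Conclusion.** The point holds as a small, definite flaw in a descriptive derivation. As written, an interruption counted without a resumed dose has no duration, and cumulative off-drug time due to AEs is understated.

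Where interruptions are open only because dosing ended, the effect on the mean is slight to modest: 0.03, 0.24, 0.66 and 2.36 weeks for underlying means of 4, 8, 12 and 24 weeks. The effect on the cumulative total is larger, at about 12% to 50%. If some interruptions never resume and remain in the count, the mean is affected more.

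All these sizes rest on assumed visit timing, start times and durations. The every-12-week dosing that some participants receive after Week 24 is not modelled. The direction for the cumulative total does not rest on these assumptions. The primary analysis and the sample size are unaffected.

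**What to change.** Amend the duration paragraph of SAP Section 4.6.2 as follows.

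- Compute duration as resumed-dose date minus missed-dose visit date plus 1.
- With no resumed dose, end the interruption at the earliest of the permanent-discontinuation date, the ED visit or Visit 18 (Week 60), and flag it as not resumed.
- Do not use the fallback in Section 4.1 that ends the treatment period at the last injection when there is no early-termination visit. That date precedes the missed dose.
- Include the observed off-drug time of flagged interruptions in the cumulative duration, and report the number not resumed by arm.
- State whether an interruption that ends in permanent discontinuation stays in this table or moves to the permanent-discontinuation summary.

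A Kaplan-Meier median time to resumption, with flagged interruptions censored, is optional.

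The cost is SAP wording and one derived flag. The case report form is not among the documents, so availability of the dates should be confirmed. The Visit 18, ED and discontinuation dates are already used elsewhere in the SAP.

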4.6.2.1. Serious Adverse Events

An individual listing of all AEs including preexisting conditions will be provided. A separate listing will include AEs that led to permanent discontinuation from the study drug.

With the International Conference on Harmonisation (ICH) E2A guideline, a SAE is any AE that results in 1 of the following outcomes:

- death
- initial or prolonged inpatient hospitalization
- a life-threating experience (that is, immediate risk of dying)
- persistent or significant disability/incapacity
- congenital anomaly/birth defect
- considered significant by the investigator for any other reason

The number and percentage of patients who experienced any ICH-defined SAE will be summarized by treatment group during the treatment and follow-up periods using the MedDRA PT nested within SOC. The SAEs will be summarized by treatment group using MedDRA PT without SOC. An individual listing of all SAEs will be provided.

4.6.2.2. Allergic Reactions and Hypersensitivities

The current standard MedDRA Standardized Medical Queries (SMQs) to search for relevant events will be used. TEAEs are characterized as follows:

- Anaphylactic reaction SMQ (20000021)
- Hypersensitivity SMQ (20000214)
- Angioedema SMQ (20000024).

The frequency and percentage of patients experiencing treatment-emergent hypersensitivities will be summarized by treatment arm, SMQ, and PT during the Treatment Period. The frequency and percentage of patients experiencing treatment-emergent hypersensitivities will also be summarized by treatment arm and timing category.

Exposure-adjusted incidence rates (per 100 PYs) of treatment-emergent hypersensitivities will be summarized.

Total number of patients who experienced the TEAE for each PT while they were on Peresolimab will be divided by the sum of all patients' time (in 100 years) of Peresolimab

exposure during the treatment period. The entire time on the study during the Peresolimab treatment period will be used to calculate the patient's time of exposure.

The time to onset of first treatment-emergent hypersensitivity during the Treatment Period and the duration of each treatment-emergent hypersensitivity during the Treatment Period will also be defined and calculated in the same way.

A by-patient listing of all treatment-emergent hypersensitivities will be provided.

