Section 4.6.2	• Added definitions of baseline for Period 2 and other periods.	Baseline definition will be different between Period 2 and other periods.
	Added additional condition for TEAE. AEs occurring on the	AE data do not include time of onset.

	date of first injection are considered as TEAE. AEs occurring on date of other injections are considered as post-injection except for the first injection date. • Removed paragraph for	To avoid redundancy due to the
	common TEAEs with ≥1%.	sample size per treatment group.
	Added definition of AESI.	• Clarification
Section 4.6.2.2	Removed "Event maps to PT of Infusion related reaction"	Not relevant to the trial.
Section 4.6.2.4	• Removed analyses for infections categorized Grampositive/negative bacterial infection, mixed aerobicanaerobic bacterial infection, fungal infections, viral infections, other infections, and opportunistic infections as assessed by the investigator.	• Not relevant to the trial.
Section 4.6.2.4		• Clarification
	Added analyses plan for herpes simplex.	Clinical request
Section 4.6.2.5	Added SMQ for malignancies	• Clarification
Section 4.6.2.6	Added SMQ for depression	• Clarification
Section 4.6.3	Added categorization for shifts of hepatic measures, hematology, lipid effects, and renal function.	• Clarification
Section 4.6.4.4	Added definitions for immunogenicity analysis	• Clarification
		• Not informative analysis given the sample size
Section 4.7.4	Added analysis plan for Japanese subgroup analysis	To prepare Japanese submission.
Appendix 4	Added definition of handling missing data for preexisting conditions and medical history	Clarification

Appendix 5	Added definition of handling	Clarification
	missing data for prior and	
	concomitant medication	
Appendix 10	Added list of PTs for herpes	• To provide a full list of PTs.
	zoster, herpes simplex, and	
	hepatitis B virus	
Appendix 11	Added definition of grade for	To provide categorization for shift
	hematologic events, lipid	tables.
	effects, and renal function	

Statistical Analysis Plan (SAP) Version 3 based on the protocol dated 31 May 2023 was approved prior to the final database lock and includes the following changes. Minor corrections/additions may not be included.

Section	Description of Change	Change Rationale	
Section 1.2 & 4.1	• Replaced "early termination" to "early discontinuation", and "ET" to "ED"	To use the consistent terminology as per study protocol.	

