1.2. Study Design

Study KDAF is a Phase 2b, randomized, double-blind, placebo-controlled study to determine the appropriate dose and dosing frequency of peresolimab in adult participants with moderately-to-severely active RA.

[figure not shown]
This study includes a

- Period 1: screening period occurring approximately 1 to 42 days prior to Period 2
- Period 2: 12-week double-blind, placebo-controlled treatment period
- Period 3: 48-week double-blind treatment period, and
- Period 4: posttreatment follow-up period occurring 4 and 12 weeks from last treatment period visit (Week 60) or Early Discontinuation Visit.

See the Schedule of Activities (SoA) in the protocol for visit schedule, procedural and assessment details.

In the remainder of this statistical analysis plan (SAP), the first 12 weeks in Period 3 (that is, Weeks 12 to 24) will be referred as Period 3A and the last 36 weeks in Period 3 (that is, Weeks 24 to 60) as Period 3B for an analysis purpose. Combined Periods 2 and 3 will be referred as the Treatment Period (Weeks 0 to 60).

Figure KDAF.1.1 describes the study design for the treatment periods (Periods 2 and 3).

[figure not shown]

Abbreviations: CDAI = Clinical Disease Activity Index; SC = subcutaneous injection; Q4W = every 4 weeks; Q12W = every 12 weeks.

Note: At Week 12, participants receiving placebo Q4W will begin receiving either 400 mg or 1000 mg peresolimab Q4W. At Week 24, participants receiving 400 mg or 1000 mg peresolimab Q4W may be switched to Q12W dosing following assessment of CDAI scores.

Figure KDAF.1.1 Study design.

Participant population

Treatment period design

- 100 mg of peresolimab every 4 weeks (Q4W)
- 400 mg of peresolimab Q4W
- 1000 mg of peresolimab Q4W
- placebo Q4W up to Week 12 followed by 400 mg of peresolimab Q4W, and
- placebo Q4W up to Week 12 followed by 1000 mg of peresolimab Q4W.

Participants randomly assigned to placebo Q4W at Week 0

At Week 12, participants receiving placebo Q4W will begin receiving either 400 mg or 1000 mg peresolimab Q4W based on randomization at Week 0. Treatment assignment will be blinded, and the participants will continue their assigned peresolimab dose and dosing frequency until the end of the study.

Participants randomly assigned to 100 mg peresolimab at Week 0

Participants receiving 100 mg peresolimab will continue their assigned dose and dosing frequency throughout the duration of the treatment period. No changes will occur.

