4.6.2. Adverse Events

AEs are recorded in the eCRF. Each AE will be coded to System Organ Class (SOC) and Preferred Term (PT), using the *Medical Dictionary for Regulatory Activities* (MedDRA) version that is current at the time of database lock. Severity of AEs is recorded as mild, moderate, or severe.

A treatment-emergent adverse event (TEAE) is defined as an event that first occurred or worsened in severity after baseline and on or prior to the earliest of the visit study drug disposition dates or the last visit date during the treatment period, whichever occurred first, and up to 50 days after study treatment discontinuation. Baseline for Period 2 is defined as all preexisting conditions recorded at Visit 1 and any AEs recorded before the first dose of study intervention. Baselines for other periods are defined as unresolved AEs just prior to the first dose of each period. The MedDRA Lowest Level Term (LLT) will be used in defining which events

are treatment-emergent. The maximum severity for each LLT will be used as baseline. If an event is preexisting during the baseline period for Period 2, but it has missing severity, and the event persists during the treatment period or up to 50 days after treatment discontinuation, then the baseline severity will be considered mild for determining any postbaseline treatment-emergence (that is, the event is treatment-emergent unless the severity is coded mild at postbaseline). If an event occurring postbaseline has a missing severity rating, then the event is considered treatment-emergent. Should there be insufficient data for an AE start date to make this comparison (for example, the AE start year is the same as the treatment start year, but the AE start month and day are missing), the AE will be considered treatment-emergent. For events occurring on the day of the first dose of study treatment, Week 0 (V2) in most cases, the events will be assumed to occur posttreatment and considered as TEAE. For events occurring on the day of doses except for the first dose of study treatment, the events will be considered to occur prior to the study drug injection.

In general, summaries will include the number of patients in the safety population (N), frequency of patients experiencing the event (n), and relative frequency (that is, percentage; n/N*100).

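### The same-day AE rule places reactions on later dosing days before the injection, so a hypersensitivity reaction to the first peresolimab dose at Week 12 is attributed to placebo and per-dose timing is distorted

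*SAP*

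**What the plan says.** SAP 4.6.2.2 lists the hypersensitivity outputs: a frequency table by arm, SMQ and PT over the Treatment Period, exposure-adjusted rates, time to first onset, a by-patient listing, and a further table in which "treatment-emergent hypersensitivities will also be summarized by treatment arm and timing category". The visible text gives neither the categories nor the reference point from which timing is measured.

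SAP 4.6.2 sets a rule for AEs dated on a dosing day. On the day of the first dose of study treatment, "the events will be assumed to occur posttreatment and considered as TEAE". On every other dosing day the rule reverses: "the events will be considered to occur prior to the study drug injection". The SAP version history gives the reason in its row for Section 4.6.2: "AE data do not include time of onset".

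Two other provisions interact with the rule. SAP 4.6.2 fixes the later baselines: "Baselines for other periods are defined as unresolved AEs just prior to the first dose of each period". SAP 1.2 gives the placebo sequences, one of which is "placebo Q4W up to Week 12 followed by 400 mg of peresolimab Q4W"; the other moves to 1000 mg at the same week.

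**The concern.** Hypersensitivity is an adverse event of special interest in SAP 4.6.2 and stands first among the potential risks in Protocol 2.3.1. Protocol 6.1 has participants observed for at least an hour after dosing, so same-day reactions are actively looked for. A rule that then dates them before the injection works against the purpose of that observation.

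The rule turns on the first dose of study treatment, not the first dose of peresolimab. For participants randomised to placebo these are 12 weeks apart. Their first contact with the active drug is therefore handled as an ordinary later dose, and a reaction to it on the same day is attributed to the treatment they have just left. This makes placebo look worse and peresolimab look better on an event of special interest.

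For everyone else, an acute reaction on re-exposure would be recorded as a late reaction to the preceding dose, if the timing table works dose by dose. A reader could then conclude that immediate reactions occur only at the first dose, when the rule itself produced that pattern.

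**Working it through.** The plan states no figure to reproduce. The check applies the SAP 4.6.2 rule to the dosing calendar.

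**Inputs**
- Same-day rule: SAP 4.6.2, current text.
- Q4W dosing from Week 0, with Period 2 running to Week 12 and the Week 12 dose opening Period 3: SAP 1.2. The Period 2 doses are at Weeks 0, 4 and 8.
- Placebo group of approximately 120 participants: SAP 5.
- Week of the last dose: not visible. Assumed to be Week 56, with Week 60 as the alternative.

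**(a) Switch from placebo at Week 12**
1. The Week 12 injection is the first peresolimab dose for these participants but their fourth dose of study treatment (Weeks 0, 4, 8, 12).
2. A reaction dated that day is therefore treated as before the injection, and so belongs to Period 2, where the group is summarised as placebo.
3. If it has not resolved, it meets the Period 3A baseline definition, so it is not emergent in Period 3A unless it worsens.
4. The exposure-adjusted rate in SAP 4.6.2.2 counts patients with an event while on peresolimab. An event treated as preceding the first peresolimab injection can be left out of that numerator.
5. Size per event: one additional participant moves the Period 2 placebo percentage by 1/120 = 0.8 percentage points.

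**(b) Lag from the most recent injection**

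Under the rule, lag = onset date minus the date of the last injection treated as preceding the event.
- First dose, same-day onset: lag = 0 days.
- Any later Q4W dose, same-day onset: the event precedes that injection, so lag = 4 × 7 = 28 days.
- Q12W, same-day onset, counting peresolimab injections only: lag = 12 × 7 = 84 days.
- Onset on the day after any dose: lag = 1 day, unaffected.

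| Span on Q4W | Dosing days | Days that can give lag 0 |
|---|---|---|
| Period 2, Weeks 0 to 8 | 8/4 + 1 = 3 | 1 of 3 |
| Weeks 0 to 56 (assumed last dose) | 56/4 + 1 = 15 | 1 of 15 |
| Weeks 0 to 60 (alternative) | 60/4 + 1 = 16 | 1 of 16 |

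These are counts of dosing days, not of reactions.

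**The case against.** The strongest reply is that the timing table need not be anchored on each injection. SAP 4.6.2.2 does not define its categories. Elsewhere the SAP measures time to first onset from the first injection (4.6.2.4, which 4.6.2.2 appears to follow) or uses intervals within the Treatment Period (4.6.2.5, 4.6.2.6). On those readings the same-day rule matters only on days that bound an interval. This stands, and it is why consequence (b) is conditional. Consequence (a) does not depend on the timing table.

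It can also be said that the rule sits in the TEAE paragraph and was written for treatment emergence and period assignment. That is fair, but period assignment is exactly where the Week 12 problem arises.

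Third, the absence of onset times is known only from a rationale entry in the version history, while the TEAE definition in Protocol 9.3.5 presupposes a recorded time of onset. Protocol text not visible here, such as 8.3.3, might also provide for separate collection of reaction timing. If such data exist the problem shrinks, but no visible SAP text says they override the rule. The version history also summarises the rule in different words; the current text of 4.6.2 governs and nothing is drawn from that difference.

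Two stronger readings are tempting and should be resisted. A reader might infer that acute reactions to later doses vanish from the safety report. They do not: they occur after the first dose of study treatment, so they remain treatment-emergent and stay in the overall SMQ/PT table and the by-patient listing. A reader might also turn 14 of 15 dosing days into a statement that 93% of same-day reactions are misclassified. That needs equal risk at every dose, Q4W throughout and a last dose at Week 56, none of which the visible text establishes.

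**Conclusion.** The point holds as a defect of attribution, not of ascertainment. On the current wording of SAP 4.6.2, a same-day hypersensitivity reaction to the first peresolimab dose after placebo is assigned to the placebo period, becomes Period 3A baseline if unresolved, and can be omitted from the peresolimab exposure-adjusted rate. Approximately 120 participants could be exposed to this. Whether an event actually leaves the rate depends on how being on peresolimab is programmed, which the SAP does not settle.

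If timing is measured from each injection, the rule also leaves only the first dose able to give a lag of 0 days, and shifts other same-day reactions by a full dosing interval. Reactions starting the day after a dose keep a lag of 1 day.

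The documents give no reaction rate and no distribution of onset by dose, so the share of reactions affected cannot be stated. The conclusion rests on the visible text having no exemption for hypersensitivity and no other source of onset timing.

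**What to change.** In SAP 4.6.2.2:
1. Define the timing categories relative to the most recent injection.
2. State that a hypersensitivity event dated on any dosing day counts as after that day's injection, unless a recorded onset time shows that it began earlier. Apply this to the timing table and to period and treatment attribution, including the Week 12 switch from placebo.
3. Reconcile the statement that AE data carry no onset time with the TEAE definition in Protocol 9.3.5, and say which data, if any, may be used to show earlier onset.

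The general same-day rule in 4.6.2 can stay for other events.

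The cost is a short definition, one sentence and a programming flag. The downside is small: a few events that truly began before the injection on a dosing day would be classed as after it, which is the cautious direction for this topic.
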